**Exclusion Criteria**

- Under age 13
- History of breast cancer (screen by past medical history)
- History of undiagnosed vaginal bleeding (screen by past medical history)
- Head trauma that affected pituitary function (screen by past medical history)
- Prolactin insufficiency (screen by past medical history)
- Previous lactation failure (defined as no lactation within 5 days postpartum)
- Any contraindication to lactation/implant use including diseases transmittable by breast milk (screen by past medical history)
- Liver dysfunction (screen by past medical history)
- Use of drugs that inhibit lactation (screen by medical history)
- Sensitivity to the components of the ENG implant (screen by past medical history)
- Contraindications to use the implant by the (US MEC) (screen by past medical history)
- Active labor
- Delivery at  $<$  37 weeks gestational age

There is a description of different inclusion/exclusion criteria between the sites. UNM Is recruiting minors under age 18 and over the age of 13, and the University of Utah is not recruiting minors. This is the only difference in the protocols.

4.3. This study will include pregnant adolescent and adult women. This study will not recruit adults who are unable to consent or women who are incarcerated.

4.4. This study will recruit women who can speak and read English and/or Spanish fluently.

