**5. Number of Subjects**

5.1 NA

PROTOCOL TITLE: Effect of immediate versus standard postpartum insertion of the contraceptive implant on breastfeeding outcomes

5.2. This is a multi-site study. Through the University of New Mexico Hospital, its affiliated clinics and the University of Utah and its affiliated clinics. We will recruit up to 200 participants between both study sites.

5.3. Up to 200 participants will be enrolled, with a goal of 75 in each group, to ensure adequate power to determine the primary outcome, after anticipated loss to follow up.

This study is a non-inferiority trial designed to demonstrate that immediate postpartum insertion of the ENG implant is non-inferior to standard ENG implant insertion with respect to the proportion of women who discontinue breastfeeding by 8 weeks after delivery. Discontinuation of breastfeeding under the current treatment, standard insertion, is expected to be 30% based on previous studies (10, 15). To achieve 80% power with a 1-sided Type 1 error of 5% utilizing the Z test (unpooled), 62 participants are required in each group for a total of 124. Accounting for expected loss to follow up of 20%, the total number of participants required is 149, rounded to 150. We intend to enroll up to 200 participants due to unanticipated loss to follow up, so this should ensure that we have enough data for data analysis.

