- For patients enrolled postpartum, the research coordinator will randomize the patient as soon after consent is signed or verbally agreed to and within 22 hours after birth to ensure implant placement for those randomized to the immediate group within 24 hours. For those who verbally agree, we will make an effort to obtain written consent via mail, e-mail, or eConsent in the UNM HSC REDCap system.
- The reproductive health physician on call will be notified to ensure placement of the implant within 24 hours; after hours, the reproductive health physician on call will also have access to the randomization sequence and will notify the research coordinator of the subject's identification number.

**PROTOCOL TITLE: Effect of immediate versus standard postpartum insertion of the contraceptive implant on breastfeeding outcomes**

*Implant insertion*

- The implant will be placed in accordance with the Federal Drug Administration (FDA) label instructions and only by providers who have completed the Merck training and are certified to insert the implant by Merck.
- Those allocated to the immediate group will obtain their implant in the hospital, by residents with attending supervision, fellows, attendings or certified nurse-midwives, and by obtaining the implant through the hospital pharmacy or the implants from the Family Medicine grant or LARC Mentoring Program for UNM participants.
- For those randomized to the standard insertion group, the implant will be provided in clinics as per clinic protocol. For UNM participants without insurance or those whose insurance does not cover immediate implant insertion, a limited number of implants (33) will be provided through the Family Medicine grant and additional implants will be available via the LARC Mentoring Program. UNM and University of Utah have established a process to enter all clinical study data via REDCap.

*Follow-up procedures:*

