## 13.Data Analysis

13.1 We will conduct a primary analysis per protocol and a secondary analysis per intention to treat. The rationale behind this strategy is to analyze both approaches and examine the result for consistency. A Repeated measures ANOVA analysis will be used for continuation of breastfeeding. To evaluate secondary outcomes between the two

**PROTOCOL TITLE:** Effect of immediate versus standard postpartum insertion of the contraceptive implant on breastfeeding outcomes

groups we will use the T-test, Wilcoxon Rank Sum test, Chi-squared test, or Fisher's exact test as appropriate. Secondary outcomes to be evaluated are to compare time of exclusivity of breastfeeding, mix breastfeeding, factors associated with discontinuing breasts feeding, time of breastfeeding discontinuation and patient satisfaction with postpartum contraception counseling and with timing of placing the implant between both groups. If there are significant differences between treatment groups, multivariable linear (for continuous outcomes) and logistic (for dichotomous outcomes) regression will be utilized in addition to control for confounding.

13.2 This study is a non-inferiority trial designed to demonstrate that immediate postpartum insertion of the ENG implant is non-inferior to standard ENG implant insertion with respect to the proportion of women who fail to breastfeed by 8 weeks after delivery. The failure rate for continuation of breastfeeding under the current treatment, standard insertion, is expected to be 30%.

The following sample size determination and plan for data analysis was developed in conjunction the University of New Mexico Clinical and Translational Science Center (CTSC). The non-inferiority margin for both primary outcomes is 15%, meaning that immediate insertion can be regarded as non-inferior (in terms of breastfeeding continuation) to standard insertion if the difference in rate with immediate insertion is no more than 15% worse than with standard insertion. To achieve 80% power with a 1-sided Type 1 error of 5% utilizing the Z test (unpooled) 62 participants are required in each group for a total 124. Accounting for the expected loss of follow up of 20%, the total subjects 149, round to 150. We intend to enroll up to 200 participants due to unanticipated loss to follow up, so this should ensure that we have enough data for data analysis.

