## **20. Recruitment Methods**

20.1. (Also described under “procedures” in Section 12.) Patients may be recruited in the following locations/timeframes: 1) antenatal clinics, 2) visits to OB-Triage 2) on admission to L&D for delivery not in active labor or 4) during the first postpartum hours in the Ob-Gyn ward of the UNM Hospital and University of Utah Hospital.

- Patients may be asked for their contraceptive choice in any of these four venues, although ideally in antenatal clinics during prenatal care. When women decide on an implant as a postpartum contraceptive in any of these venues, the PCP (Ob-Gyn, Family Medicine physicians/residents and midwives) may discuss the patient’s interest in hearing about the study and may contact the research coordinator by a message in the EMR or by phone or in person to let her know that the patient is interested in hearing about the study.
- Additionally, the research coordinator will review antenatal clinic, OB Triage and inpatient (L&D and postpartum) lists to assess patients’ contraceptive plan through review of the EMR. The research coordinator may contact patients who have decided on a postpartum implant to assess her interest in participating in the study.
- If the patient expresses interest, the research coordinator will present the study and ask the patient for her interest in enrolling. If interested, the research coordinator and/or a study co-investigator will explain the study, screen the patient for eligibility and obtain informed written or electronically signed consent.
- Women will not be approached for study participation if they are in active labor. Women will be approached and enrolled, if interested, either prior to active labor (e.g., when admitted for induction of labor or scheduled cesarean delivery) or after delivery.
- We will not enroll patients who are under sedation. Most participants will be enrolled and undergo informed consent in the antenatal period; some will be

**PROTOCOL TITLE:** Effect of immediate versus standard postpartum insertion of the contraceptive implant on breastfeeding outcomes

enrolled when they are admitted to labor and delivery not in active labor; neither of these two groups would be under sedation. For those “up to 22 hours after delivery,” we will only enroll women who have not received sedation within a 4-hour period.

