## **22. Economic Burden to Subjects**

22.1. Participant's third party payer (i.e. insurance company) is responsible for all the costs related to the implant and clinical treatment. This would be the case regardless of study involvement.

New Mexico Medicaid reimburses for immediate postpartum implant placement (prior to hospital discharge) and will cover all costs related to the implant and clinical treatment. Private insurers do not cover the costs. We will be enrolling participants that are Medicaid, uninsured, underinsured and private insurers, until the supply of 33 implants run out. We do anticipate receiving additional no-cost implants; if this occurs, we will continue enrollment of private insured and un or under-insured women. Please see the table below.

Research Procedures	Number of Samples/Procedures	Responsible Party	
		Study	3rd Party Payer or Participant
Immediate implant insertion	75		
			
			

PROTOCOL TITLE: Effect of immediate versus standard postpartum insertion of the contraceptive implant on breastfeeding outcomes

_____	_____		
_____	_____		
_____	_____		
_____	_____		
_____	_____		
Standard of Care Procedures		Number of Samples/Procedures	Responsible Party
Implant insertion at 4-6 weeks		75	Study  3rd Party Payer or Participant 
_____	_____		
_____	_____		
_____	_____		
_____	_____		
_____	_____		
_____	_____		
_____	_____		
_____	_____		

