22.2. No other costs to participants are anticipated

22.3. The participants and/or the third party will be charged for the implant device in case the participant cannot afford the implant or the implant is not covered by the third party (insurance) for the immediate insertion, there will be 33 of implants out of charge paid by a private grant. Additional implants are available via the LARC Mentoring Program, However, this is subject to availability and once the product is out of stock no more implants will be available from the grant or the LARC Mentoring Program.

22.4. Participants will not be billed for the cost of tests and procedures directly associated with this study. However, reimbursement for all related costs of care will be sought from the patient's insurer, managed care plan, or other benefits program. If they do not have insurance, they may be responsible for these costs. Patients will also be responsible for any associated co-payments or deductibles required by their insurance.

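### Section 22 ties enrolment to payer and a finite free-implant stock, but the eligibility list and the randomisation step do not, so payer-related non-receipt can fall mainly on the immediate arm

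*Combined protocol and SAP*

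**What the plan says.** Section 22.1 states that New Mexico Medicaid reimburses placement before discharge and that private insurance does not. It continues: "We will be enrolling participants that are Medicaid, uninsured, underinsured and private insurers, until the supply of 33 implants run out". Enrolment of privately insured, uninsured and under-insured women goes on after that if more no-cost implants arrive. Section 22.3 adds that supply from both free sources is finite: "once the product is out of stock no more implants will be available from the grant or the LARC Mentoring Program".

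Section 12.2 (Implant insertion) says whom the free implants serve: "For UNM participants without insurance or those whose insurance does not cover immediate implant insertion, a limited number of implants (33) will be provided". It names the LARC Mentoring Program as a further source for the same women, without a number.

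The inclusion and exclusion lists in section 4.2 contain no criterion on cover or supply. On the sites, the text after the lists says that Utah does not recruit minors, and then: "This is the only difference in the protocols".

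On timing, section 20.1 says: "Most participants will be enrolled and undergo informed consent in the antenatal period". Section 12.2 (Randomization) has the coordinator obtain the assignment from REDCap shortly after admission for birth or, for women enrolled postpartum, within 22 hours of delivery. No check of cover or stock is described.

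Section 15.1 allows a woman who does not follow study procedures, placement of the implant among them, to be withdrawn without her consent. Section 13.1 makes the per-protocol analysis primary and intention to treat secondary.

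**The concern.** A rule that decides who can receive one of the two assigned treatments appears only in the section on costs. Staff confirm eligibility against the inclusion and exclusion criteria (section 25.1.1), so the limit need not be applied where it matters. Even if it is applied at enrolment, that is the wrong moment for a woman enrolled in pregnancy, because the stock may be gone when she is admitted and randomised.

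Insurer refusal is described only for immediate insertion. A privately insured woman assigned to immediate insertion may miss the 24-hour window for lack of an implant, while a similarly insured woman assigned to standard insertion does not meet that refusal. Loss of this kind occurs after randomisation and is related to payer. In the per-protocol analysis it can make the arms differ in payer mix. In an intention-to-treat analysis that keeps these women, it places unexposed women in the immediate arm and pulls the difference toward zero, which favours a non-inferiority claim.

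**Working it through.** **1. The sections side by side.** Section 22.1 holds a payer- and stock-linked limit on enrolment. Section 4.2 and the randomisation text in section 12.2 hold none. Enrolment is mostly antenatal and assignment is at admission. A woman can therefore satisfy section 4.2, be enrolled while stock lasts, and be assigned when none is left. For Utah, section 12.2 ties the free sources to UNM participants, section 22.1 describes New Mexico Medicaid only, and section 33.1 names the UNM Hospital pharmacy as the store for immediate insertion.

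**2. The plan's own sample size.** Inputs: "To achieve 80% power with a 1-sided Type 1 error of 5% utilizing the Z test (unpooled), 62 participants are required in each group" (section 5.3), 30% discontinuation under standard insertion (sections 5.3 and 13.2), and a 15-point margin (section 13.2). With discontinuation rates p_S and p_I:

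n = [p_S(1−p_S) + p_I(1−p_I)] × (1.645 + 0.842)² / (0.15 − (p_I − p_S))²

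- Equal arms at 30%: 0.42 × 6.18 / 0.0225 = 115.4, so 116 per group.
- p_I = 25%, which is not printed: 0.3975 × 6.18 / 0.04 = 61.4, so 62 per group.

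The stated 62 is not reproduced from the printed inputs with equal arms. That is a separate matter and this point does not depend on it. I use 62 below only as the plan's evaluable number per arm.

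**3. How far the grant stock goes.** The share of women without cover, u, is not in the documents and is assumed. If free implants go only to the immediate arm, 33 suffice while u ≤ 33/75 = 44%, or 33/100 = 33% if 200 are enrolled. If they also served the standard arm, the limits would be 33/150 = 22% and 33/200 = 16.5%. With no stop on enrolment and no further stock, at 75 per arm:

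| u | needed | short of 33 | share of arm without implant (q) |
|---|---|---|---|
| 40% | 30 | 0 | 0% |
| 50% | 37.5 | 4.5 | 6% |
| 60% | 45 | 12 | 16% |
| 70% | 52.5 | 19.5 | 26% |

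**4. Intention to treat.** Take a true 15-point harm among recipients, let non-recipients have the standard-arm rate, and suppose all are followed to 8 weeks. Then p_I = 0.30 + 0.15(1−q). At q = 10%, p_I = 0.435:

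- SE = √[(0.21 + 0.2458)/62] = 0.0857
- z = (0.15 − 0.135)/0.0857 − 1.645 = −1.47, so the false non-inferiority rate is 7.1%, against 5.0% at q = 0.

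The same formula gives 8.6% at q = 16% and 11.7% at q = 26%. From stock-out alone, q = 10% would need u = (33 + 7.5)/75 = 54% at 75 per arm, or (33 + 10)/100 = 43% at 100.

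**5. Per protocol.** Let d be the continuation rate of the women lost minus that of the women who stay, with 70% continuation overall. The retained immediate arm then has 0.70 − q·d. With d assumed at ±20 points, q = 10% shifts it by 2 points and q = 26% by 5.2 points, against a 15-point margin. If the lost women continue longer, the shift works against non-inferiority; if they stop sooner, it favours it. The documents give neither d nor its sign.

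**The case against.** The strongest reply is that section 22.1 already restricts non-covered enrolment once free stock is gone, so the plan is not without a limit. That is correct. What remains is that the limit is absent from section 4.2 and acts before the time of assignment.

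A reader might infer that non-receipt falls on the immediate arm only. The documents do not support that. The standard arm depends on a clinic visit, and the background (section 2.3, on satisfaction with timing) says many women miss postpartum follow-up. Section 22.4 leaves uninsured women possibly responsible for costs, and the table in 22.1 charges payer or participant in both arms. Only the insurer-refusal route is specific to immediate insertion, so the net imbalance cannot be derived.

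A reader might also take 33 as the whole supply. It is the grant stock alone: the LARC Mentoring Program adds to it, section 22.1 expects more, and section 9.3 reports about 200 UNM women a year-type cohort of 3000 deliveries receiving the implant before discharge. Lack of cover is also not the same as non-receipt, since a participant may be charged.

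Third, a reader might infer a per-protocol bias of known size. An uncovered share of 20%, for example, is 15 of 75 or 20 of 100 women, which the grant stock covers at UNM; loss on that scale would have to arise at Utah, whose share is not given. The intention-to-treat figure also needs non-recipients to be followed, whereas section 15 withdraws them and uses data already collected.

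On Utah, silence does not show that no source exists. That site has its own IRB review, and the sentence on site differences follows one about eligibility criteria rather than billing.

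**Conclusion.** The point holds as a mismatch between sections with a statistical consequence. Followed as written, the plan can assign an uncovered woman to an insertion for which no implant has been confirmed, then withdraw her and lose her from the primary analysis for a payer-related reason. Such loss can fall mainly, though not exclusively, on the immediate arm.

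Size and direction are open, because payer mix, LARC stock and Utah cover are not given. The 44% and 33% limits assume grant stock alone, used only for the immediate arm. The rise from 5.0% to 7.1% assumes 62 per arm, a true 15-point harm, 10% non-receipt, non-recipients with the standard-arm rate, and complete follow-up. It is an illustration, not an estimate. The change should be made because the loss is preventable at little cost; confidence in its practical importance is medium.

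**What to change.** Carry the section 22.1 limit into sections 4.2 and 12 for both sites: immediately before REDCap releases the assignment, and identically for every woman, confirm that an implant for in-hospital placement is covered by her payer or in stock. Because the check precedes assignment, it cannot unbalance the arms.

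State Utah's source of implants, or limit non-covered enrolment to UNM, and bring the sentence on site differences into line. Record payer and the reasons for non-receipt by arm, and keep following non-recipients for the 8-week outcome so that the intention-to-treat analysis can include them; section 15 needs matching wording.

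Reserving a free implant for each non-covered woman from antenatal enrolment is not needed. It would tie up stock for women later assigned to standard insertion and could halt non-covered enrolment early.

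The cost is protocol wording, one field at randomisation, a stock count and some extra follow-up. Some non-covered women will not be randomised once stock is used, as section 22.1 already intends.

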22.2. No other costs to participants are anticipated

22.3. The participants and/or the third party will be charged for the implant device in case the participant cannot afford the implant or the implant is not covered by the third party (insurance) for the immediate insertion, there will be 33 of implants out of charge paid by a private grant. Additional implants are available via the LARC Mentoring Program, However, this is subject to availability and once the product is out of stock no more implants will be available from the grant or the LARC Mentoring Program.

22.4. Participants will not be billed for the cost of tests and procedures directly associated with this study. However, reimbursement for all related costs of care will be sought from the patient's insurer, managed care plan, or other benefits program. If they do not have insurance, they may be responsible for these costs. Patients will also be responsible for any associated co-payments or deductibles required by their insurance.

### 23. Compensation

In return for the participant's time and the inconvenience of participating in this study, the participant will be paid a total of \$40 to participate in this research study. This incentive will be divided in two gift cards of \$20. The first gift card will be given at the time of enrollment. The second gift card of \$20 will be given after completing the 8 week follow up. In the event that timeline of compensation is changed, the research team will send a letter to the affected participants to notify them of the change. Participants that have surpassed the new date of compensation will be paid immediately and those who have not will be paid at the time of completion of the surveys at that time.

### 24. Compensation for Research-Related Injury

In the event that the patient has an injury or illness that is caused by participation in this study, patients will be verbally reminded of the following during the consent

**PROTOCOL TITLE:** Effect of immediate versus standard postpartum insertion of the contraceptive implant on breastfeeding outcomes

process: reimbursement for all related costs of care will be sought from the patient's insurer, managed care plan, or other benefits program. If they do not have insurance, they may be responsible for these costs. Patients will also be responsible for any associated co-payments or deductibles required by their insurance.

